3 RESEARCH OBJECTIVES AND OUTCOME VARIABLES

Research Objectives	Outcome Variables
Primary	
To inform the frequency of women at higher FNAIT risk among pregnant women of different racial and ethnic characteristics who present for pre-natal care.	The number of participants that are determined to be at higher FNAIT risk compared to the total number of pregnant women assessed for higher FNAIT risk, with attention to self-characterized race and ethnicity.
Secondary	
To inform the frequency of HPA-1a alloimmunization among pregnant women identified at higher FNAIT risk.	Occurrence of anti-HPA-1a maternal alloimmunization at Week 10 postpartum ^a
To inform the frequency of pregnancy outcomes among pregnant women identified at higher FNAIT risk.	
 • Rate of spontaneous abortion, defined as non-deliberate fetal death which occurs prior to 19 weeks of gestation • Rate of elective abortion, defined as deliberate termination of pregnancy at any time in gestation • Rate of stillbirth, defined as non-deliberate fetal death anytime in gestation on or after 19 weeks of gestation • Rate of premature birth, defined as live birth prior to 37 completed weeks of gestation • Rate of live births (≥ 37 completed weeks of gestation)
To inform the frequency, where data are available, of neonatal thrombocytopenia in infants born to women who have alloimmunized, as determined by detectable anti-HPA-1a antibody at Week 10 postpartum. ^a	Neonatal thrombocytopenia and severe neonatal thrombocytopenia, as determined by a platelet count $< 150 \times 10^9/L$ and $< 50 \times 10^9/L$ respectively, within 72 hours of birth, where data are available

^a For pregnancies that do not result in a live birth, the assessment of alloimmunization will be at 10 weeks from the date of the pregnancy-terminating event (ie, abortion [spontaneous/elective] or stillbirth).

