4.2.1 Gestation Week 10 to 14 Pre-natal Visit Assessments

- Maternal demographics: year of birth, weight, height, and self-characterized race and ethnicity
- Gestational age in weeks as estimated by the principal investigator
- Obstetric history: mode of delivery, gestational age of delivery, live birth, abortion
- Blood samples will be collected (refer to the study Laboratory Manual for details):
 1. Maternal HPA-1 genotype
 2. Maternal HLA-DRB3*01:01 genotype
 3. Maternal anti-HPA-1a antibodies
 4. Fetal HPA-1 genotype

It is preferred that all samples be collected at the Gestation Week 10 to 14-visit. If all blood samples cannot be collected during one visit, the collection can be split into 2 timepoints. The first timepoint should include blood samples for maternal HPA-1 genotype, maternal HLA-DRB3*01:01 genotype and the maternal anti-HPA-1a antibodies and must be collected at the Gestation Week 10 to 14-visit. The second timepoint should include blood samples for the fetal HPA-1 genotype and should be collected by 18 weeks of gestation.

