3 STUDY DESIGN

3.1 Study Overview

This is a prospective, non-interventional, natural history study open to all pregnant women presenting at a Gestation Week 10 to 14 prenatal visit at the involved institutions. At this pre-natal visit, the participant will be invited to provide informed consent and blood samples will be collected for determining whether the woman is at higher risk for the occurrence of HPA-1a alloimmunization, as described in [Table 2](#).

Table 2 Pre-Natal FNAIT Laboratory Testing at Gestation Week 10 to 14

Test No.	Test	Description	Result	Protocol Specific Action
1	Maternal HPA-1 genotype	Test will identify women who are HPA-1b/b, indicating risk for HPA-1a sensitization and occurrence of FNAIT	1a HPA-1b/b (HPA-1a negative)	Perform Test 2
			1b HPA-1a/b HPA-1a/a	None – no further testing
2	Maternal HLA-DRB3*01:01 genotype	Test will identify women who are HLA-DRB3*01:01 positive, indicating higher FNAIT risk	2a HLA-DRB3*01:01 positive	Perform Test 3
			2b HLA-DRB3*01:01 negative	None – no further testing
3	Maternal anti-HPA-1a antibody	Test will establish women who have no detectable anti-HPA-1a antibody	3a Anti-HPA-1a antibody negative	Perform Test 4
			3b Anti-HPA-1a antibody positive	None – no further testing
4	Fetal HPA-1 genotype	A cell-free fetal DNA (cffDNA) test to inform on the presence of the antigenic stimulus for maternal alloimmunization	4a HPA-1a/b	Will be followed for final assessments
			4b HPA-1b/b	None – no further testing

DNA = deoxynucleic acid; FNAIT = fetal and neonatal alloimmune thrombocytopenia;
HLA = human leukocyte antigen; HPA = human platelet antigen

[figure not shown]
If the participant meets the study-specific blood test results, ie, genotype HPA-1b/b, genotype HLA-DRB3*01:01 positive, anti-HPA-1a antibody negative, and carries an HPA-1a positive fetus ([Table 2](#), Test Results 1a, 2a, 3a, and 4a), a follow-up determination will be made at Week 10 postpartum on the occurrence of HPA-1a alloimmunization, pregnancy outcome and, for participants who have alloimmunized, the occurrence of neonatal thrombocytopenia (where data are available).

CONFIDENTIAL

For participants, who meet the study specific tests results (ie, Test Results 1a, 2a, 3a, and 4a in [Table 2](#)) but the pregnancy does not result in a live birth, the assessment of alloimmunization will be at 10 weeks from the date of the pregnancy-terminating event (ie, abortion [spontaneous/elective] or stillbirth).

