3.2.1 Baseline Screened Population

The Baseline Screened Population consists of all enrolled participants who meet Inclusion/Exclusion criteria (Inclusion Criteria: Pregnant women (≥ 18 years of age) who have provided informed consent for the study; Exclusion Criteria: Prior history of FNAIT), and who have complete final FNAIT screening tests results.

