5.2 General Presentation Considerations

As this study is intended to be descriptive in nature, no hypotheses will be tested.

Continuous variables will be summarized using means and SD or medians and IQRs, as appropriate. Continuous data that is expected to be skewed will be presented in terms of the maximum, median, minimum and number of observations.

The SD will be reported to two more decimal places than the raw data recorded in the database. In general, the maximum number of decimal places reported shall be four for any summary statistic.

Discrete variables will be summarized using numbers and percentages. Categorical data will be summarized in terms of the number of participants providing data at the relevant time point (N), frequency counts and percentages.

Percentages will be presented to one decimal place. Percentages will not be presented for zero counts except two situations: 1) Comparison of OMB classification of race and ethnicity between Baseline Screened Population and Alloimmunization Follow-up Population; 2) Summary of race and ethnicity by OMB classification in Alloimmunization Follow-up Population. Percentages will be calculated using N as the denominator.

Confidence intervals will be presented to one more decimal place than the raw data. Confidence intervals for proportions will be calculated using the exact (Clopper-Pearson) method, unless stated otherwise.

All report outputs will be produced using SAS® version 9.4 or a later version in a secure and validated environment. All report outputs will be provided to the Sponsor in a single Microsoft Word document.

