5.3 Statistical Methods and Analyses to be Performed

The proportion of FNAIT laboratory test subgroups among Baseline Screened Population or Alloimmunization Follow-up Population will be presented with their respective 80%, 90% and 95% confidence intervals.

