5.3.2 Analysis of the Baseline Screened Population

The proportion of participants at higher risk for HPA-1a alloimmunization will be determined from the Baseline Screened Population and summarized descriptively.

The proportion will be calculated as (the number of participants determined at baseline to be at higher risk for HPA-1a alloimmunization) / (all enrolled participants who meet Inclusion/Exclusion criteria and who have complete final FNAIT screening tests results, as defined in Section 3.2.1). Listing for participants who are HPA-1b/b, HLA-DRB3*01:01 positive and HPA-1a alloantibody negative at baseline (Baseline Screened Population) and listing for Participants who are HPA-1b/b, HLA-DRB3*01:01 positive and HPA-1a alloantibody positive at baseline (Baseline Screened Population) are provided for publication purposes.

In addition to the above, maternal demographics, obstetric history and other baseline characteristics will be analyzed, including:

- Age at screening and BMI
- Obstetric History will be summarized by 1 or more prior pregnancies, 2 or more prior pregnancies, 3 or more prior pregnancies, and 4 or more prior pregnancies (including history of prior pregnancies with mode of delivery, pregnancy outcomes)
- Proportion of participants by region, by self-characterized classification of race and ethnicity or by race (White vs. Others), and by OMB classification of race and ethnicity
 - With attention to region (Europe vs. North America), first vs. second or later pregnancy, self-characterized classification of race and ethnicity or by race (White vs. Others), and OMB classification of race and ethnicity
 - With attention to region (Europe vs. North America) and then further broken down by OMB classification of race and ethnicity
- Proportion of participants who are HPA-1b/b
 - With attention to region (Europe vs. North America), first vs. second or later pregnancy, self-characterized classification of race and ethnicity or by race (White vs. Others), and OMB classification of race and ethnicity
- Proportion of participants who are HPA-1b/b and HLA-DRB3*01:01 positive
 - With attention to region (Europe vs. North America), first vs. second or later pregnancy, self-characterized classification of race and ethnicity or by race (White vs. Others), and OMB classification of race and ethnicity
- Proportion of participants who are HPA-1b/b, HLA-DRB3*01:01 positive and HPA-1a alloantibody negative

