5.4 Study Participants

The alloimmunization study populations are characterized in the flowchart (Figure 2). Consented participants are those that have provided informed consent for the study. Eligible participants are those that meet protocol inclusion and exclusion criteria.

Figure 2 Flowchart of Participant Disposition

A clear accounting of the disposition of all participants who enter the study will be provided, from initial consent to study completion. This will include the numbers of the following groups:

- Number of participants consented
- Number of eligible participants
- Number of participants confirmed HPA-1b/b (vs. HPA-1aa or HPA-1a/b)
- Number of HPA-1b/b participants confirmed HLA-DRB3*01:01 positive (vs. negative)
- Number of HPA-1b/b and HLA-DRB3*01:01 positive participants who are HPA-1a alloantibody negative (vs. positive)
- Number of HPA-1b/b and HLA-DRB3*01:01 positive participants who are HPA-1a alloantibody negative and who have an HPA-1a positive fetus (vs. HPA-1b/b fetus)
- Number of HPA-1b/b and HLA-DRB3*01:01 positive participants who are HPA-1a alloantibody negative and have an HPA-1a positive fetus and who are assessed for presence of HPA-1a alloantibodies at 10 weeks postpartum
- Number of participants missing expected FNAIT Laboratory results as described by the testing sequence and their prior test result(s)

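### Because testing is sequential, the requirement for complete screening results drops only HPA-1b/b women after Test 1, so any loss at Tests 2 to 4 lowers the primary frequency

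*SAP*

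**What the plan says.** SAP 3.1, Table 2, sets four tests in sequence: maternal HPA-1 genotype, maternal HLA-DRB3*01:01, maternal anti-HPA-1a antibody, and fetal HPA-1 genotype. A woman who is HPA-1a/a or HPA-1a/b at Test 1 stops there, with the action "None – no further testing". The same action applies to HLA-negative women after Test 2 and to antibody-positive women after Test 3.

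SAP 3.2.1 admits to the Baseline Screened Population only eligible women "who have complete final FNAIT screening tests results". SAP 5.3.2 makes this the primary denominator: "all enrolled participants who meet Inclusion/Exclusion criteria and who have complete final FNAIT screening tests results". It lists the HPA-1b/b, HLA-positive, antibody-negative and HPA-1a-positive-fetus proportions under the same population. Completeness is not defined. The protocol's denominator (section 3) has no such condition: "the total number of pregnant women assessed for higher FNAIT risk".

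On timing, protocol 4.2.1 prefers one visit for all samples but allows a split: "The second timepoint should include blood samples for the fetal HPA-1 genotype and should be collected by 18 weeks of gestation". Protocol 4.2.1.1 requests a further fetal-genotype sample from women who qualify on Tests 1 to 3.

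On missing data, SAP 5.6.2 rules out imputation and leaves participants with many missing values to a decision before database lock. SAP 5.3.4 plans no sensitivity analysis. SAP 5.4 reports a count of women lacking a result that their earlier results made necessary.

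**The concern.** A completeness rule is harmless when every woman faces the same number of tests. Here a non-case usually needs one result and a case needs four. Each extra test is another chance to be excluded, and after Test 1 that chance falls only on HPA-1b/b women. A missing Test 4 falls only on women one step from being counted as a case.

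The rule also reaches the earlier stages. A woman with a valid HPA-1b/b genotype but no fetal result leaves even the HPA-1b/b frequency. That sits poorly with protocol 5.4, which includes data up to withdrawal of consent.

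At stake are the primary outcome and its breakdown by race, ethnicity and region, which is the study's main purpose. If completion of Tests 2 to 4 differs between groups, the comparison is distorted as well as the level. The quarterly runs in SAP 5.7 could be affected more, while later tests are still pending.

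**Working it through.** **Inputs from the documents.** HPA-1b/b about 2% in Caucasian women, HLA-DRB3*01:01 positive about 27%, HPA-1a-positive fetus about 85% (protocol section 2). Enrolment 20,000 to 30,000, with 30 to 50 women at higher risk (SAP 5.8). Exact intervals (SAP 5.2) at three levels: "respective 80%, 90% and 95% confidence intervals" (SAP 5.3).

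**Assumptions.** m1 to m4 are the shares missing at Tests 1 to 4 among women due that test, and are unrelated to the pending result. All HLA-positive women are taken as antibody negative at baseline.

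**The plan's own figure.** 30/20,000 = 0.150% and 50/30,000 = 0.167%. The product 2% x 27% x 85% = 0.459% gives 92 to 138 women, so 30 to 50 is not reproduced. It would need an HPA-1b/b frequency of about 0.65% to 0.73%. A racially mixed sample could explain part of that, but the documents give no such input. This is a separate matter: the relative falls below are nearly the same at 0.459% and 0.160%.

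**Base case.** 25,000 women and 40 cases (0.160%). HPA-1b/b frequency = 0.00160/(0.27 x 0.85) = 0.697%, or 174.3 women, of whom 47.06 are HLA positive.

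**Effect of the rule.** Reported frequency = 40(1-m2)(1-m3)(1-m4) / (25,000 - women removed). The removed women barely change the denominator, so the relative fall is close to 1-(1-m2)(1-m3)(1-m4).

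| Assumed m2 / m3 / m4 | Cases / denominator | Frequency | Change |
|---|---|---|---|
| 0 / 0 / 1% | 39.6 / 24,999.5 | 0.158% | -1.0% |
| 0 / 0 / 5% | 38.0 / 24,997.6 | 0.152% | -5.0% |
| 0 / 0 / 10% | 36.0 / 24,995.3 | 0.144% | -10.0% |
| 0 / 0 / 20% | 32.0 / 24,990.6 | 0.128% | -20.0% |
| 5% / 5% / 10% | 32.5 / 24,984.8 | 0.130% | -18.7% |

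**HPA-1b/b frequency.** With 10% lost at Test 4, 0.27 x 0.10 = 2.7% of HPA-1b/b women drop out. With 5%/5%/10% it is 0.05 + 0.95 x 0.27 x (0.05 + 0.95 x 0.10) = 8.7%.

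**Loss at Test 1.** With m1 = 5% alone, 38/23,750 = 0.160%: no bias. With m1 = 1% and m4 = 10%, 250 women are lost at Test 1 and 4.7 at Test 4. HPA-1b/b women are then (250 x 0.00697 + 4.7)/254.7 = 2.5% of those removed (7.0% if HPA-1b/b is 2%).

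**Sampling error.** The exact 95% interval for 40/25,000 is 0.114% to 0.218%; the exact 80% interval is 0.129% to 0.198%. Every row lies inside the 95% interval. The 20% fall (0.128%) is just below the 80% lower limit.

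**Group comparison (illustration).** With equal true frequency but Test 4 completion of 95% in one region and 80% in another, the ratio of reported frequencies is 0.80/0.95 = 0.84.

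**Alternatives, with 10% lost at Test 4.**
- Stage product: (174.3/25,000) x 0.27 x (36/42.35) = 0.160%, since 47.06 - 4.71 = 42.35 women have a Test 4 result.
- Unresolved women kept as non-cases: 36/25,000 = 0.144%, no improvement.
- All 4.7 unresolved women counted as cases: 40.7/25,000 = 0.163%.

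**The case against.** A reader might infer that the rule removes potential cases almost exclusively. The documents do not support that. Women without a Test 1 result are removed too, at least 98% of them HPA-1a carriers on the protocol's Caucasian figure, and they could easily be the majority of exclusions. Their loss is roughly proportionate, so it neither causes nor cancels the bias.

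A reader might also infer that the frequency is known to be materially low. It is not: no missing rate is given, and several provisions limit the loss.
- Samples for Tests 1 to 3 must be taken at the Week 10 to 14 visit, so loss at Test 2 or 3 after a valid Test 1 would be mainly a laboratory or sample problem.
- One visit is preferred for all four samples, so loss of the pregnancy before the fetal draw matters mainly when collection is split.
- Protocol 4.2.1.1 gives a second opportunity for the fetal result, although the documents do not say whether either result alone is enough.
- SAP 5.6.1 keeps samples taken after Week 18, so lateness alone does not exclude a woman.

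The study is also descriptive ("no hypotheses will be tested"), and SAP 5.4 will make the losses visible.

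All of this stands, and it lowers the likely size. It does not remove the mechanism. Neither the disposition count nor a decision before lock enters the estimate, and a confidence interval describes sampling error, not systematic loss. Protocol 10.1 also notes that, at study start, the central laboratory running the other tests had no validated fetal assay, so some loss at Test 4 is plausible.

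**Conclusion.** The concern holds in a limited form. Followed as written, the rule biases the primary frequency and the earlier stage frequencies downward whenever results at Tests 2 to 4 are missing independently of what they would have shown. If missingness depends on the pending result, the size and even the direction could change.

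The size rests wholly on assumed rates, from negligible when nearly all expected tests are done to about a fifth in the heavier scenarios. The conclusion also takes completeness to mean every result expected under the sequence. That is the only workable reading, since requiring all four tests would exclude every HPA-1a carrier, and the SAP 5.4 count supports it. Severity: should-fix. The effect is conditional and of unknown size, but it bears on the primary outcome and its subgroup comparisons.

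**What to change.** 1. In SAP 3.2.1, define complete as having every result expected under the Table 2 sequence.
2. For each stage, use as denominator the eligible women due that test who have a valid result. The HPA-1b/b frequency then uses all women with a Test 1 result.
3. Estimate the overall primary frequency as the product of the four stage proportions, with a bootstrap or delta-method interval. Keep the planned proportion and its Clopper-Pearson interval as supportive.
4. In sparse race or ethnicity subgroups, the product interval collapses at zero cases, or a later stage becomes 0/0. There, report the planned proportion with its exact interval, plus bounds that count unresolved women as all non-cases and then as all cases. Restrict the bounds to women with a Test 1 result: counting 250 women lost at Test 1 as cases, beside about 40 true cases, would make the upper bound useless.
5. Report missing counts by stage, region and race/ethnicity.

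No new data are needed. The cost is SAP wording and modest programming, an overall interval that is no longer exact, and an assumption that missing results are ignorable given earlier tests. Bounds widen when loss occurs early: in the 5%/5%/10% scenario about 15.2 women are unresolved, giving 32.5/25,000 = 0.130% to 47.7/25,000 = 0.191%.

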3.2.2 Alloimmunization Follow-up Population

The Alloimmunization Follow-up Population consists of all participants identified at screening to be at higher risk for HPA-1a alloimmunization (i.e., HPA-1b/b, HLA-DRB3*01:01 positive, anti-HPA-1a antibody negative, carrying an HPA-1a positive fetus), and who have a Week 10 postpartum HPA-1a alloimmunization test result.

4 DATA SOURCE

The primary data source for this study will be the raw data which is collected by Cisiv and FNAIT laboratory data from GCL Electronic Data Capture (EDC). Source documents provide evidence for the existence of the participants and substantiate the integrity of the data collected. Source documents are filed at the investigator's site.

Data reported on the case report form (CRF) or entered in the electronic CRF (eCRF) that are transcribed from source documents must be consistent with the source documents or any discrepancies must be explained. The investigator may need to request previous medical records or transfer records, depending on the study. Also, current medical records must be available. Definition of what constitutes source data can be found in the Source Data Agreement (eg, Site Trial Binder, other site communications).

5 STATISTICAL METHODS

5.1 Data Quality Assurance

All tables, figures, and listings to be included in the report will be independently checked for consistency, integrity and in accordance with standard Parexel procedures for analysis and reporting.

The data for the planned analysis will be quality controlled as per applicable Parexel standard operating procedures. The data extraction will be set to an appropriate date so that all data cleaning activities which include any corrections will have been already completed.

Where required, a process has been carefully implemented to onboard any useful SOPs originally designed to govern the delivery of primary/secondary data studies for regulatory submission to be used for natural history studies.

5.2 General Presentation Considerations

As this study is intended to be descriptive in nature, no hypotheses will be tested.

Continuous variables will be summarized using means and SD or medians and IQRs, as appropriate. Continuous data that is expected to be skewed will be presented in terms of the maximum, median, minimum and number of observations.

The SD will be reported to two more decimal places than the raw data recorded in the database. In general, the maximum number of decimal places reported shall be four for any summary statistic.

Discrete variables will be summarized using numbers and percentages. Categorical data will be summarized in terms of the number of participants providing data at the relevant time point (N), frequency counts and percentages.

Percentages will be presented to one decimal place. Percentages will not be presented for zero counts except two situations: 1) Comparison of OMB classification of race and ethnicity between Baseline Screened Population and Alloimmunization Follow-up Population; 2) Summary of race and ethnicity by OMB classification in Alloimmunization Follow-up Population. Percentages will be calculated using N as the denominator.

Confidence intervals will be presented to one more decimal place than the raw data. Confidence intervals for proportions will be calculated using the exact (Clopper-Pearson) method, unless stated otherwise.

All report outputs will be produced using SAS® version 9.4 or a later version in a secure and validated environment. All report outputs will be provided to the Sponsor in a single Microsoft Word document.

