5.8 Determination of Sample Size

It is anticipated that approximately 20,000 to 30,000 participants will be enrolled with the goal of identifying approximately 30 to 50 pregnant women at higher risk for HPA-1a alloimmunization. Of the women identified to be at higher risk for HPA-1a alloimmunization, it is anticipated that approximately 10 to 20 may alloimmunize to HPA-1a.

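### One decimal place is too coarse for a primary frequency planned at about 0.15% to 0.17%, and the precision of its confidence limits is not clearly defined

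*SAP*

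**What the plan says.** SAP 5.2 fixes the format of percentages: "Percentages will be presented to one decimal place". The only exceptions it names concern whether a percentage is shown beside a zero count.

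Confidence limits have their own rule: "Confidence intervals will be presented to one more decimal place than the raw data". The section does not say what the raw data are for a proportion. For standard deviations it refers to recorded values: "The SD will be reported to two more decimal places than the raw data recorded in the database". It also sets a ceiling: "In general, the maximum number of decimal places reported shall be four for any summary statistic". Intervals for proportions are exact (Clopper-Pearson) by default.

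SAP 5.3 asks for the proportions in the laboratory test subgroups to be "presented with their respective 80%, 90% and 95% confidence intervals". I take this to include the primary proportion, which is defined by those tests. SAP 5.3.2 describes it: "The proportion of participants at higher risk for HPA-1a alloimmunization will be determined from the Baseline Screened Population and summarized descriptively".

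SAP 5.8 gives the planned number of women at higher risk: the study enrols "with the goal of identifying approximately 30 to 50 pregnant women at higher risk for HPA-1a alloimmunization". The enrolment behind that yield is 20,000 to 30,000. Protocol 4.1.1 gives the same counts. Neither document writes out the implied percentage.

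**The concern.** One decimal in percent is a grid of 0.1 percentage points. That suits the Follow-up Population, where percentages are large, but the primary frequency is itself only one to three grid steps from zero. Rounding can move the printed estimate by up to 0.05 points, which is a large part of its value.

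The SAP also asks for three confidence levels. If the format prints the same limits at all three, two of them tell the reader nothing. The primary objective is a frequency across racial and ethnic groups, and both documents expect a lower HPA-1b/b frequency in some of them. The same format applies to those breakdowns, and several of the tables are meant for publication.

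**Working it through.** **Inputs.** Women at higher risk: 30 to 50. Enrolled: 20,000 to 30,000 (SAP 5.8, Protocol 4.1.1). Method: Clopper-Pearson (SAP 5.2). Levels: 80%, 90%, 95% (SAP 5.3). I use the enrolled number as the denominator; the Baseline Screened Population would be somewhat smaller.

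**Step 1, implied frequency.** The documents state no percentage to reproduce. Pairing low with low and high with high:
- 30/20,000 = 0.150%
- 40/25,000 = 0.160% (midpoint)
- 50/30,000 = 0.167%

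The extreme pairings are 30/30,000 = 0.100% and 50/20,000 = 0.250%.

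**Step 2, exact limits.** With α = 1 − level, the lower limit is the α/2 quantile of Beta(x, n − x + 1) and the upper limit is the 1 − α/2 quantile of Beta(x + 1, n − x). In percent:

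| x/n | 80% | 90% | 95% |
|---|---|---|---|
| 30/20,000 | 0.116–0.192 | 0.108–0.203 | 0.101–0.214 |
| 40/25,000 | 0.129–0.198 | 0.121–0.208 | 0.114–0.218 |
| 50/30,000 | 0.137–0.201 | 0.130–0.211 | 0.124–0.220 |
| 30/30,000 | 0.077–0.128 | 0.072–0.136 | 0.067–0.143 |
| 50/20,000 | 0.206–0.302 | 0.195–0.316 | 0.186–0.329 |

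**Step 3, printed at one decimal.** With half-up rounding, the first three estimates print as 0.2%, and all nine of their intervals print as 0.1 to 0.2. At 30/30,000 the result is 0.1% with 0.1 to 0.1 at every level. At 50/20,000 (also a rounding tie) it is 0.3% with 0.2 to 0.3 at every level.

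The coincidence is common but not universal. For each whole count from 30 to 50, all three intervals print identically for 16 of the 21 counts at each of N = 20,000, 25,000 and 30,000. At N = 20,000, for example, 37 to 41 women give intervals that differ at least in part.

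**Step 4, size of the rounding.** A printed 0.2% covers 30 to 49 women of 20,000, or 45 to 74 of 30,000. The largest rounding error is 0.05 points. For 40/25,000 the half-width is (0.218 − 0.114)/2 = 0.052 points at 95% and (0.198 − 0.129)/2 ≈ 0.034 at 80%. Rounding can therefore be about as large as the statistical uncertainty.

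**Step 5, the other reading of the interval rule.** If limits carry one decimal more than the printed percentage, they have two:

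| x/n | 80% | 90% | 95% |
|---|---|---|---|
| 30/20,000 | 0.12–0.19 | 0.11–0.20 | 0.10–0.21 |
| 40/25,000 | 0.13–0.20 | 0.12–0.21 | 0.11–0.22 |
| 50/30,000 | 0.14–0.20 | 0.13–0.21 | 0.12–0.22 |

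The levels now differ, but the estimate beside them is still 0.2%, which lies at or close to the upper limit.

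Two decimals are not sufficient everywhere. At 30/30,000 the 90% and 95% intervals both print as 0.07 to 0.14. Three decimals separate all three levels for every count from 30 to 50 at the three values of N.

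**Step 6, subgroups (assumption).** The documents give no subgroup sizes. If a group had 3,000 women and one at higher risk, 1/3,000 = 0.033% would print as 0.0%.

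**The case against.** The strongest reply is that nothing is lost. SAP 5.2 requires N and frequency counts beside the percentage, and SAP 5.4 adds a count at each screening step. A table showing 40, N = 25,000 and 0.2% lets any reader recover 0.160% and recompute the intervals. This stands. A reader might infer that the primary estimate cannot be read from the planned output; the documents do not support that.

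Second, the interval rule is ambiguous. One decimal is the more literal reading, because counts and genotype categories have none and the section ties raw data to recorded values. But the SAP does not say so for proportions, and a two-decimal reading separates the intervals in the three main cases. The collapse of the three levels is therefore conditional on the reading. The loss in the point estimate is not.

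Third, the printed 0.2% depends on the pairing. SAP 5.8 does not pair low with low: 30/30,000 prints correctly as 0.1%, and 29/20,000 (0.145%) would also print as 0.1%. This limits the example, not the point, since the three intervals coincide at both extreme pairings too.

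Fourth, a reader might infer that a later trial sizing its screening from 0.2% would fall a quarter short: 1/0.002 = 500 screened per case against 1/0.0015 = 667. That needs a planner who ignores the count and N in the same table, and it takes the extreme case on a rounding tie. At 50/30,000 the shortfall is 1 − 500/600 = 17%; at 30/30,000 there is none.

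Fifth, it is tempting to say that group differences below 0.1 points vanish. Rounding can also enlarge them: 0.14% and 0.16% print as 0.1% and 0.2%.

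**Conclusion.** The concern holds as a reporting defect. A stated rule, with no exception for the primary frequency, prints that frequency on a grid too coarse for its planned size. On the literal reading of the interval rule, the three confidence levels print identically at 30/20,000, 40/25,000, 50/30,000 and both extreme pairings. On the two-decimal reading only the estimate is affected.

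The four-decimal sentence does not cure this, because it is a ceiling and does not override the one-decimal rule for percentages.

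The consequence is lost precision in the printed primary result. No estimand, denominator, method or dataset is affected. The effect may be larger in race or ethnicity groups with lower frequency, but the documents give no sizes from which to quantify that. The conclusion assumes that observed counts fall near those planned, that rounding is half-up, and that the screened denominator is close to enrolment.

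**What to change.** Add one sentence to SAP 5.2. Proportions at higher risk, and other screening proportions expected below 1%, with the Baseline Screened Population or a subgroup of it as denominator, are shown to at least two decimals in percent, or per 10,000 women. Their confidence limits carry the same, explicitly stated precision. Keep one decimal elsewhere, including the Follow-up Population and the HPA-1b/b proportion where it is near 2%.

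Two decimals are enough at 30/20,000, 40/25,000 and 50/30,000. If the sponsor wants the three levels to remain distinct at the lower frequencies as well, use three decimals, or one decimal per 10,000. Both options stay within the four-decimal maximum.

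The cost is a sentence in the SAP and a format change in the affected tables. No new data or analysis is needed. The only drawback is mixed precision between tables, which a footnote can explain.
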